30 hospitals (conditional on the response rate) will be randomized into an order for a stepped wedge cluster randomized trial. The stepped wedge trial randomizes hospitalist participants at the group level (i.e., hospital) rather than the individual level (i.e. hospitalist). We will use a stepped-wedge trial design for two reasons: 1) individual-level randomization risks misclassifying patients, contaminating unexposed physicians, and failing to address group-level attitudes to and practices of ACP; 2) a parallel cluster randomized design risks imbalance among groups because of the high intra-class correlation coefficient that exists for billing practices at the hospital-level. Each group 'crosses over' from control to intervention at a randomized timepoint and multiple 'time steps' of data collection occur. All the Sound-affiliated hospitalists at each hospital will be invited to use the video game intervention. If a participant accepts, the participant will receive an iPad with the video game pre-loaded. The iPad will be mailed to either a participant's home address or the hospital site where it will be distributed by the clinical performance nurse or nurse liaison. We will contact and consent a small sample of 20-30 physicians who completed the efficacy portion of the trial for a semi-structured interview via Zoom to discuss their experiences playing the game. These semi-structured interviews will be recorded and transcribed, and participants will be compensated with a \$50 Amazon gift card for

participating in the interview. All data will be collected through the game itself with Google Analytics and Qualtrics. This data will be linked with Sound data and with Medicare claims that is regularly and continually collected by those external parties. Finally, we will ask Sound to abstract the charts of a random sample of 200-300 patients treated by trial physicians, so that we can test the validity of our outcome measures.

4. Analysis

Please see the Statistical Analysis Plan

5. Study Progress Monitoring

This study will be overseen by a Data Safety and Monitoring Board. The DSMB has been empaneled. It will be approved and the first meeting will be held before the start of the trial. In the process of establishing the DSMB charter, DSMB members will provide guidance on safety surveillance and reporting requirements.

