As determined by NIH, the DSMB will “1) periodically review and evaluate the accumulated study data for participant safety, study conduct and progress, and, when appropriate, efficacy, and 2) make recommendations to NIDCR concerning the continuation, modification, or termination of the trial. The DSMB considers study-specific data as well as relevant background knowledge about the disease, test agent, or patient population under study.”

As described by NIH, “The DSMB is responsible for defining its deliberative processes, including: event triggers that would call for an unscheduled review, stopping procedures that are consistent with the protocol, unmasking (unblinding), and voting procedures. The DSMB is also responsible for maintaining the confidentiality of its internal discussions and activities as well as the contents of reports provided to it.

The DSMB should review each protocol for any major concern prior to implementation. During the trial, the DSMB should review cumulative study data to evaluate safety, study conduct, and scientific validity and integrity of the trial. As part of this responsibility, DSMB members must be satisfied that the timeliness, completeness, and accuracy of the data submitted to them for review are sufficient for evaluation of the safety and welfare of study participants. The DSMB should also assess the performance of overall study operations and any other relevant issues, as necessary.”

All eligible participants will be contacted at the start of the trial and receive the interventions as described under Section 3. The trial will run for a total of 6 months.

6. Risks & Benefits

Note: Risks may be physical, psychological, social, legal, economic, to reputation, or others.

a. Describe any potential risks, their likelihood and seriousness:

There are two categories of participants in this pragmatic trial: 1) Consented research participants (hospitalists); and 2) Unconsented research participants (patients of participating hospitalists).

The consented research participants are the hospitalists employed by Sound Physicians. A *key consideration in this study that the participants' employer is a partner in conducting the trial.* The primary outcome is the hospitalists' behavior; specifically, the frequency with which hospitalists bill for ACP conversations with patients 65 and older.

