Sound Physicians is a national physician practice that employs acute care providers in hospital medicine, emergency medicine and critical care. We selected this physician practice as a partner in our efforts to test the effect of the video game for three reasons: 1) it staffs over 200 hospitals with a wide variety of geographic and organizational characteristics, increasing the generalizability of our observations; 2) it has already implemented best-practice quality improvement efforts to improve ACP practices at its hospitals, including providing employees with web-based didactic education on the importance of ACP in the hospital and a small financial incentive (\$20) for each documented ACP conversation that meets Medicare's criteria for reimbursement; 3) billing practices remain lower than desired.

We will selectively sample 30-40 hospitals that contract with Sound Physicians, and will randomize them to the step in which they receive the intervention. We will stratify randomization based on hospitals' baseline characteristics (e.g., number of providers, region, baseline ACP billing rate). We will generate randomization schemas using Stata 13.0 (Statacorp, College Station, TX, USA) statistical software, using random block sizes of 4. Although we cannot blind study personnel and participants, we will mask the arm and group assignment during the analysis phase.

b. Provide a justification of the proposed sample size

For the **Efficacy condition**, we plan to recruit 120 physicians at 30 hospitals (conditional on willingness to participate) and will expose them sequentially to the video game intervention. If fewer physicians per hospital agree to participate, we will plan to increase the number of hospitals allocated to the efficacy trial.

Assuming a baseline ACP rate of 14% (rising by 1.25%/quarter), a hospital intra-class correlation coefficient of 0.008-0.115, and 160 patients/physician/quarter, with 120 physicians, we can detect a 3% difference between ACP practices before and after the distribution of the intervention with an alpha of 0.05 and 80% power.

For the **Effectiveness condition**, we will recruit 170 hospitals. This represents the remainder of the Sound hospitals. As part of our agreement with the funding agency, we are to deliver the intervention to all Sound hospitalists. The effectiveness study, therefore, is not specifically powered.

c. Define the target population:

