The target population is physicians whose job responsibilities include ACP. In this study, all inpatient hospitalist physicians who have worked for Sound Physicians at a study hospital for at least one quarter are eligible to participate. There are approximately 200 hospitals across the US providing a total of approximately 2000 eligible hospitalists. The study aims to balance the sample in the following characteristics:

- A hospital's ACP billing rate.
- Number of hospitalists at a hospital.
- If the hospital is an academic medical center.
- Availability of Clinical Performance Nurse to pull charts.

Additionally, the inclusion criteria are: a hospitalist must have worked for Sound for at least 6 months, report use of ACP billing codes, provide contact information that matches a contact in our list of eligible physicians (i.e. full name match or partial name match and employer-based email match), and receive a working iPad. If participants do not meet any of these criteria, they will be informed that they are ineligible, but that they may play the video game intervention voluntarily and without compensation for their time. They will receive instructions on how to download and play the game, as well as complete the post-game questionnaire. Communications with eligible and ineligible participants may be modified if a participant contacts the study team directly with specific questions or concerns. The response will be modified to address the participant's needs.

d. Vulnerable populations

Note: Certain populations are considered vulnerable to coercion and undue influence and are provided with additional protections when participating in a research study.

Identify any of the below populations which you plan to recruit for this study. In addition, complete the form(s) linked with each population as necessary and upload on the 'Supporting Documents' page in Rapport.

- [Pregnant Women, Fetuses and Neonates](#)
- [Children](#)
- [People with impaired decision-making capacity](#)

The following populations may also be considered vulnerable to coercion or other undue influence:

- Prisoners
- People who are economically disadvantaged
- The elderly
- People who are illiterate or do not speak English
- Students and employees

Describe any other potentially vulnerable population(s) and the additional protections provided to them:

Employees. See section 6.

10. Recruitment

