Describe method(s) of recruitment. Associated advertisements and other materials to be used for recruitment should be uploaded to the 'Consent Forms and Recruitment Materials' page in Rapport.

All participants will be offered the opportunity to "opt in" to participate.

Those who engage with the study procedures are provided with consent information at each step of engagement; including an agreement to proceed with pre- and post-game survey questionnaire completion on the face page of the Qualtrics surveys (efficacy); and information about the data captured by game use at the time of downloading the game App (effectiveness condition).

Recruitment and “Opt-In” Consent Process: Game Use. All Sound hospitalist participants in the efficacy condition will provide “opt-in” consent for active participation (e.g., use of the game and provision of personal information). Sound Physician leadership will introduce the research study to regional and hospital team leaders at the annual leadership conference and to all eligible hospitals via e-mail, with a web-based link to a Qualtrics survey to opt-in to study participation. We seek a waiver of documentation from the Dartmouth IRB to use electronic consent documentation.

Claims analysis. Sound hospitalist participants and their patients will not provide consent for use of their billing data. We have relevant data use agreements with Sound Physicians and CMS. We seek a waiver of informed consent from the Dartmouth IRB.

11. Informed Consent, Assent, and Authorization

All forms discussed in this section should be uploaded to the ‘Consent Forms and Recruitment Materials’ page in Rapport

a. Please describe the consent and/or assent process, addressing the following:

- Who will obtain consent/assent from participants
- Where the consent/assent process will take place
- The timeframe for providing information potential participants about a study, having the consent form signed, and beginning study activities
- Any precautions taken to minimize the possibility of coercion or undue influence
- The forms which will be used as well as any aids used to simplify scientific or technical information
- How comprehension will be ensured

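### Screened-out physicians are given the game download with no condition that their hospital has crossed over, and protocol and SAP differ on when screening occurs, so play in control periods is possible

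*Protocol*

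**What the plan says.** **Release of the game.** Protocol Section 9c requires that "a hospitalist must have worked for Sound for at least 6 months, report use of ACP billing codes", that contact details match the study's list, and that a working iPad is received. Anyone who fails a criterion is told that "they may play the video game intervention voluntarily and without compensation for their time", and "They will receive instructions on how to download and play the game". No date, step or crossover condition is attached.

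**Timing in the protocol.** Section 5 states: "All eligible participants will be contacted at the start of the trial and receive the interventions as described under Section 3". Section 10 has leadership introduce the study "to all eligible hospitals via e-mail, with a web-based link to a Qualtrics survey to opt-in to study participation". Section 3 makes the number of hospitals to be randomized depend on the response rate, which also suggests that responses come first. Section 9b says of the recruited physicians that the study "will expose them sequentially to the video game intervention".

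**Timing in the SAP.** The Power calculation section plans recruitment of physicians for each step. The Variable Specification table treats enrollment as a phase at the hospital and groups it with the post period (coded 1) against the pre period (coded 0).

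**Analysis.** In the SAP's Primary Analysis, Game_jt is an indicator by hospital and period. The hospital as a whole is the responsible unit, and no physician identifier enters the model.

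**The concern.** Section 3 of the protocol prefers hospital-level to individual-level randomization partly because the latter risks "contaminating unexposed physicians". The download instruction could bring that contamination back inside control-phase hospitals.

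For enrolled physicians, the mailed iPad is a physical gate that can be timed to the step. A download has no such gate, and sequential exposure is promised only for those recruited. Tenure, use of ACP codes and contact match can all be failed at the survey, before any iPad is sent. Section 9c even makes such failures likely: it first describes physicians with at least one quarter of service at a study hospital as eligible, then requires six months with the employer.

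Play by these physicians before crossover would fall in periods with Game_jt = 0. If the game works, the control rate would rise and beta_2 would be pulled toward zero.

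**Working it through.** **1. Is control-phase play possible as written?**

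- *Protocol account.* Contact is at the start (Section 5), the survey link goes to all eligible hospitals (Section 10), and sequential exposure covers recruited physicians (Section 9b). A physician at a last-step hospital could answer early, be screened out and be sent the download with several control periods still to run.
- *SAP account.* Recruitment is by step, and enrollment is coded 1. Screening and any ineligibility notice then fall in exposed periods, so this route creates no control-phase play.
- Neither document states a release rule for ineligible physicians, so the answer depends on which account of recruitment is followed.

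**2. Reproducing the SAP's power figures.** The inputs from the Power calculation section are a 22% baseline rate, two-sided 0.05, ICC 0.01, k = 5 steps and b = 1 baseline period. I take t = 1 measurement per step. With n patients per hospital-period and ICC r, the stepped-wedge design effect is

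DE = (b + kt) × [1 + r(ktn + bn − 1)] / [1 + r(ktn/2 + bn − 1)] × 3(1 − r) / [2t(k − 1/k)].

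The hospital counts (30 and 40) are my assumption, chosen because they match the SAP's effective sample sizes.

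- 76,800 patients, 30 hospitals: n = 76,800/(30 × 6) = 426.7. DE = 6 × (26.59/15.92) × 0.3094 = 3.100. Effective size per group = 38,400/3.100 = 12,388 (SAP: 12,388).
- 192,000 patients, 40 hospitals: n = 800, DE = 3.137, effective size = 96,000/3.137 = 30,604 (SAP: 30,603).
- A two-proportion test with these sizes detects 1.49 and 0.95 points at 80% power (SAP: 1.5 and 1). Power for 3.5 points exceeds 99.9% (SAP: above 99%).

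The SAP's figures are reproduced.

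**3. Illustration of dilution.** Let c be the share of the full hospital-level effect d already present, on average, in control periods. The documents do not give c; the values below are assumptions. Control rate = 0.22 + c·d, intervention rate = 0.22 + d, contrast = (1 − c)d. With m = 12,388 per group:

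power = Φ{[(1 − c)d − 1.96·SE0]/SE1}, where SE0 is the pooled and SE1 the unpooled standard error.

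| c | contrast, d = 1.5 points | power | contrast, d = 3.5 points | power |
|---|---|---|---|---|
| 0 | 1.50 | 80.4% | 3.50 | >99.9% |
| 0.1 | 1.35 | 71.6% | 3.15 | >99.9% |
| 0.2 | 1.20 | 61.3% | 2.80 | 99.9% |

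At c = 0.1 and d = 1.5, for example, the rates are 22.15% and 23.5%, SE0 and SE1 are both about 0.00533, and (0.0135 − 0.01045)/0.00533 = 0.57, so Φ = 0.716.

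In the larger scenario (30,603 per group) the 1.5-point column would read 99.3%, 97.8% and 94.2%.

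This is a simple two-group approximation. A full stepped-wedge analysis weights control periods unequally, and any baseline data that precede contact carry no exposure, which holds the average c down.

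**The case against.** Several parts of the case against this point stand.

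- **The release date is not in the text.** A reader might infer that the game is released as soon as an ineligible physician responds, or that recruitment is a single e-mail. The documents say neither. Section 9c gives no timing, and Section 10 does not count the e-mails. Early release is an inference from Sections 5 and 10.
- **The later SAP points the other way.** Recruitment for each step, with enrollment coded as exposed, would close this route. The sentence in Section 5 also refers on to the stepped design in Section 3 and concerns eligible participants.
- **One criterion adds little.** A physician can fail to receive a working iPad only after distribution, which is the exposure event itself.
- **The bias is not beyond repair.** The SAP's Secondary analyses replace the hospital indicator with a measure of physicians who had played by the time they cared for the patient. That could pick up early play. It is secondary, however, individual play is not randomized, and the documents do not say whether ineligible players' data are linked.
- **The benchmark matters.** If effects simply add across physicians, early play by ineligible physicians leaves the enrolled physicians' own contribution intact. The contrast shrinks relative to a trial in which the same ineligible physicians first play at crossover, or through spillover to colleagues before crossover.

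None of this supplies the missing rule. The two documents still give different accounts of when screening happens, and only one of them protects the control periods.

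**Conclusion.** The gap is real but modest: a low-to-moderate concern. Download access for ineligible physicians is not conditional on crossover. Whether that matters depends on a conflict between the protocol (contact at the start) and the SAP (enrollment by step) that must be resolved. On the protocol's account, play in periods coded Game_jt = 0 is possible and would bias the primary contrast toward no effect. On the SAP's account it would not occur by this route.

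The size is unknown. A reader might infer a fixed percentage attenuation, but that would need the share of patients treated by ineligible early players, which the documents do not give. Nor is 1.5 points an expected effect: the SAP presents it as the smallest difference detectable at 80% power in its smallest scenario. The fall from about 80% to 72%-61% is therefore conditional on a true effect that small, on that sample size, and on 10% to 20% of the effect being present in control periods. At the SAP's 3.5-point effect power stays above 99%, and the harm would be an understated estimate.

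**What to change.** 1. In Protocol Section 9c, state that download instructions go to ineligible physicians only on or after their hospital's assigned crossover.
2. Reconcile Protocol Section 5 with the SAP's Variable Specification table and Power calculation section, so that contact and screening occur at the hospital's step.
3. Use the game analytics already collected (Protocol Section 3) to report any play before crossover, by hospital and date, noting any players who cannot be linked to a hospital. If enrollment has already closed, this part alone remains useful.

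The cost is a few sentences, a delayed e-mail and one descriptive table. Ineligible physicians wait for the link, at most for the trial's 6 months. This is a cheap improvement.

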**Statistical Analysis Plan**

**Hopewell Hospitalist: A Video Game Intervention to Increase Advance Care Planning by Hospitalists [Efficacy Trial]**

**NCT 04557930**

**11 November 2021**

## Statistical Analysis Plan

### Variable Specification

Variable type	Variable Name		Variable Format	Notes
Primary Analysis				
dependent variable	primary	acpbilled	dichotomous (0/1)	
	secondary	mortality	dichotomous (0/1)	
		length of stay	continuous	
		7-day readmission	dichotomous (0/1)	
		30-day readmission	dichotomous (0/1)	
	ICU usage	dichotomous (0/1)		
primary predictor	phase of trial at hospital		categorical [0 = pre; 1 = enrollment and post]	We will retain 3-level coding until the point of the analysis (pre 0; enrollment 0.5; post 1)
time	date		categorical with days since start of baseline period as categorical labels	Will capture an anticipated non-linear and differential impact of COVID across time
	block		categorical	Further captures the COVID effect by adjusting for differential time-trends by block. Will allow for heterogeneity as these were pre-formed and control for the same general region of the country.
patient covariates	patient age		categorical variable (65-74, 75-84, 85+)	Association between age and probability of ACP billing is continuous with no inflections at specific ages (based on graphical analysis). We considered using the continuous variable but thought that the categorical variable provides more clinical context (e.g., an OR of 1.02 per year vs. OR 1.32 for patients age 74-85 and OR 1.76 for patients with age 85+)
	Charlson comorbidity index		categorical (0 to ≥5)	

	serious illness (selected based on differences in cohort between pre/post trial period)	dichotomous (0/1)	Serious illness codes based on Kelley et al. "Identifying older adults with serious illness" 2019 J Pain Symptom Management
	illness severity (evidence of organ failure)	exclude for endogeneity	It may be difficult to parse the differences between organ failure and receipt of LST (for example - codes for respiratory failure may be equivalent to the receipt of mechanical ventilation in some institutions). Since we anticipate that stepped-wedge design takes care of differences in cohort, we exclude these codes.
	surprise question	dichotomous (0/1)	Include if available by the time we are ready to submit. Otherwise exclude for missingness.
	COVID status	dichotomous (0/1)	Based on the presence of an ICD10 diagnosis code or a flag created by the treating physician that the patient was confirmed positive.
hospital covariates	risk-adjusted ACP rate prior to the start of the trial.	continuous	The correlation between risk-adjusted ACP rate and change in ACP rate is 0.23 (and therefore the risk of collinearity is small); these variables capture distinct effects.
	change in ACP rate between Quarter 2 2019 and Quarter 1 2020	continuous	
	practice size	quartiles	
	region	categorical	
	COVID admissions – fraction of total admissions with COVID in the month of the date of admission	continuous	
	COVID prevalence - HRR-level COVID rate in the month of the date of admission	continuous	We will test for collinearity with COVID admissions and exclude based on the variance inflation factor
random effect	hospital	categorical	
Secondary Analysis (Mediation)			
mediator	completion	dichotomous (0/1)	Whether physician finished the Game
	adherence (minutes)	quartiles	Minutes playing the Game

	engagement	quartiles	Physician experience with the game as captured by the Narrative Engagement Scale (scored out of 20)
	change in attitudes	difference in median attitude score before and after exposure	We control for baseline score to separate level effects from change- variable effects
random effect	physician, hospital	categorical	
Secondary Analysis (moderation)			
moderator (hospital and physician- level)	contextual effect – site cooperation rate	continuous	consider as covariate and interaction with MD adherence; remove interaction-effect if not-significant at the 0.05-level
	opportunity – proportion of physicians seen by patient who enrolled in the trial.	continuous	The total number of physicians will be considered as an alternative specification. One additional analysis will be a repeated measures model at the patient level where we define a separate outcome for each physician encountered by the patient until an ACP conversation occurred.
	physician CME compliance	dichotomous	

Note: In situations where the effects of ordinal categorical predictors (e.g. quartiles) follow a clear monotonic pattern, we will seek to simplify the model by considering use of the underlying continuous variable as a predictor. Such simplifications will only be implemented if the addition of the continuous predictor renders its categorical counterpart highly non-significant (e.g.,  $p > 0.2$ ). The advantage of simplifying the model is that we will potentially be able to make a stronger interpretation of the results and moderation analyses will be more easily interpreted.

